#### **7.4. Lost to Follow-up**

A participant will be considered lost to follow-up if he/she repeatedly fails to return for scheduled visits and the study center is unable to contact the participant.

The following actions must be taken if a participant fails to return to the clinic for a required study visit:

- The site must attempt to contact the participant and reschedule the missed visit as soon as possible and counsel the participant on the importance of maintaining the assigned visit schedule and ascertain whether or not the participant wishes to and/or should continue in the study.
- Before a participant is deemed lost to follow-up, the investigator or designee must make every effort to regain contact with the participant (where possible, 3 telephone calls and, if necessary, a certified letter to the participant's last known mailing address or local equivalent methods). These contact attempts should be documented in the participant's medical record.

- Should the participant continue to be unreachable, he/she will be considered to have withdrawn from the study. The sponsor may retain and continue to use any data collected.
- The site should also make every effort to verify the participant's vital status with the participant's regular/non-study physician(s).

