#### 8.2.1. Clinical Evaluations

The efficacy endpoints primarily rely on the participant's clinical status with respect to death, hospitalization, mechanical ventilation, and supplemental oxygen. The primary efficacy endpoint is the proportion of participants who are alive and free of invasive mechanical ventilation through Day 28 and the key secondary endpoint is all-cause mortality at Day 28.

Two of the secondary endpoints, clinical status and time to clinical improvement, are based on the 8-point NIAID ordinal scale (see [Appendix 4](#)). In addition to death, hospitalization, mechanical ventilation, and supplemental oxygen, components of the ordinal scale also include ongoing medical care and limitations on activities. It is important for changes in each of these components to be documented with the date and time of change. Participants must be considered a 3 or 4 on the scale to be eligible for enrollment, and an improvement of  $\geq 2$  grades is considered a treatment success.

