### 9.4.1. Primary Endpoint

Phase 3: The primary analysis will utilize the ITT analysis set and a Cochran-Mantel-Haenszel test stratified by each of the actual stratification factors. Participants will be counted as failures once they go on a ventilator or die. Number and percentage of failures will be presented for each treatment arm. Cochran-Mantel-Haenszel p-values, estimated common odds ratios, estimated common risk differences, and corresponding approximate two-sided 95% CIs will be presented. The Breslow-Day test will be used to test the homogeneity of the odds ratios across strata. Although missing data are expected to be limited, any such cases will be imputed as failure. A supportive analysis using multiple imputation will be done in order to assess the sensitivity of the inference to the approach to missing data.

Phase 2: A similar methodology will be used; however, multiple imputation will not be done.

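### For a participant who stays unreachable, Section 7.4 recovers only vital status, so someone confirmed alive can still lack a primary outcome and be imputed as a failure

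*Protocol*

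**What the plan says.** Protocol Section 7.4 requires sites to try to reach a participant who misses a visit, by telephone and then by letter. If that fails, "Should the participant continue to be unreachable, he/she will be considered to have withdrawn from the study". The last bullet then adds: "The site should also make every effort to verify the participant's vital status with the participant's regular/non-study physician(s". No other outcome is named for recovery from an outside source.

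Section 8.2.1 defines the primary endpoint as the "proportion of participants who are alive and free of invasive mechanical ventilation through Day 28". Section 9.4.1 gives the matching failure rule, "Participants will be counted as failures once they go on a ventilator or die", and the missing-data rule: "Although missing data are expected to be limited, any such cases will be imputed as failure". For Phase 3, "A supportive analysis using multiple imputation will be done". For Phase 2, "A similar methodology will be used; however, multiple imputation will not be done".

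The supplied SAP covers only the analyses after the Cohort 1 or 2 lock. In Table 18, study discontinuation before Day 25 counts as an event (footnote b) and is left out of the success line (footnote a). In Table 19, footnote (a) counts it as an event in the combined mortality line. Neither table makes an exception for a participant later found to be alive.

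**The concern.** The recovery step is narrower than the endpoint it should protect. Knowing that a participant is alive settles one of the two components. Ventilation status after last contact stays unknown, and the plan's default is then failure.

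The participants at issue were not ventilated at last contact, because anyone ventilated earlier is already an observed failure. Section 7.4 applies when someone does not return to the clinic, so they are mainly people already discharged. Some true successes would then be recorded as failures although a physician was asked about the participant and could have been asked one more question.

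Equal losses in both arms shrink the treatment difference and cost power. Unequal losses bias it in either direction. Section 9.2 states no allowance for missing outcomes.

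**Working it through.** **Text check**

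| Step | Needed for the primary endpoint | What the plan obtains |
|---|---|---|
| Ordinary follow-up | Survival and ventilation | Both; Schedule of Activities footnote e asks for the date and time of ventilation start and stop |
| Participant reached by call or letter | Survival and ventilation | Both can be asked |
| Participant unreachable, physician contacted | Survival and ventilation | Survival only (7.4, last bullet) |
| Outcome still missing | n/a | Failure (9.4.1); event if study discontinuation is before Day 25 (SAP Table 18, Cohorts 1/2) |

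The gap is in the third row.

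**Inputs.** Section 9.2 gives 300 dociparstat and 150 placebo participants (450 at 2:1), failure rates of 9% and 20%, two-sided alpha 0.05, and power above 80% with a futility look. Section 9.5 gives the look after 225 completers and a bound of 0.919, read here as a Z value. The loss fraction m is an assumption.

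**The plan's own figure.** Single-stage power = Φ[(Δ − 1.96·SE0)/SE1].

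- Pooled rate = (0.20 × 150 + 0.09 × 300)/450 = 57/450 = 0.1267.
- SE0 = √[0.1267 × 0.8733 × (1/150 + 1/300)] = 0.0333.
- SE1 = √[0.20 × 0.80/150 + 0.09 × 0.91/300] = 0.0366.
- Power = Φ[(0.11 − 1.96 × 0.0333)/0.0366] = Φ(1.224) = 89.0%.

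With the futility look obeyed, the calculation is P(Z1 > 0.919 and Z2 > 1.96), with correlation √0.5. It gives 80.4% if the unpooled variance is used throughout, about 84% with a pooled test statistic and its true unpooled variance, and 87.1% if the pooled variance is used throughout. All agree with the stated figure of above 80%.

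**Missing counted as failure.** If a fraction m of otherwise event-free participants per arm is imputed as failure, then p′ = p + m(1 − p), and Δ becomes 11 points × (1 − m).

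| Assumed m, both arms | Placebo / dociparstat failure | Difference (points) | Single-stage power | Power with futility look (unpooled to pooled) |
|---|---|---|---|---|
| 0% | 20.0% / 9.0% | 11.0 | 89.0% | 80.4% to 87.1% |
| 1% | 20.8% / 9.9% | 10.9 | 86.9% | 78.0% to 84.5% |
| 2% | 21.6% / 10.8% | 10.8 | 84.7% | 75.6% to 81.9% |
| 5% | 24.0% / 13.6% | 10.5 | 77.9% | 68.6% to 74.1% |

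At 5%, imputed failures are 150 × 0.05 × 0.80 = 6 on placebo and 300 × 0.05 × 0.91 ≈ 14 on dociparstat, added to 30 and 27 expected.

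**Unequal loss (assumed).** With 2% on placebo and 5% on dociparstat, the difference is 21.6 − 13.55 = 8.1 points and single-stage power is 58.4%. Reversed, the difference is 24.0 − 10.8 = 13.2 points and power is 94.1%.

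**What the wording change can recover.** The table charges every imputed failure to this gap, so it is an upper bound. If total loss is 2% and half is recoverable (both assumed), the gain is from 84.7% to 86.9%, about 2 points.

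**The case against.** The case on the other side has real weight.

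- **Existing safeguards.** Direct contact comes first, and anyone reached can report ventilation. Section 7.3 makes follow-up through Day 28 the default and allows information to be collected from people who refuse assessments. This stands, and it limits the gap to participants who stay unreachable.
- **Multiple imputation.** It probes the missing-data rule in Phase 3. It does not change the primary result, and Phase 2 has none.
- **Who can be rescued.** Consent withdrawals and failed physician contacts stay missing, and a physician may not know of an admission elsewhere. This stands.
- **Consent.** Seeking clinical detail about someone deemed withdrawn must fit the authorization described in Section 11.1.3. This stands as a limit. However, 7.4 already seeks vital status in that situation, so outside contact is part of the plan.

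A reader might infer more than the documents support:

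- *Everyone confirmed alive is necessarily scored a failure.* Section 9.4.1 does not define when the outcome is missing. The supplied SAP applies its rule only before Day 25, and no Phase 3 SAP was supplied.
- *Power drops below 80% once loss passes about 4%.* That comes from the single-stage pooled calculation. With the futility look, the starting point already spans 80.4% to 87.1%, so the crossing point depends on the variance method.
- *Vital status at least settles mortality.* Under SAP Table 19 it does not settle the combined line.
- *Those lost are mostly recovered, or the active arm is penalised.* This is plausible for discharged participants, but the documents give no data on it.

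**Conclusion.** The gap is real: the recovery step asks for less than the primary endpoint needs, and the default for what remains unknown is failure. Some participants known to be alive, whose ventilation status could have been asked about, can be scored as failures.

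The effect cannot be fixed from the documents, which say only that missing data should be limited. The power losses under Working assume that losses are unrelated to outcome among event-free participants, are equal in both arms except where stated, and are all recoverable. They are therefore ceilings. If loss is near 1% or less, the effect is small: 86.9% against 89.0% single-stage. The change is still worth making, because it replaces an assumed outcome with a reported one whichever arm that favours.

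**What to change.** 1. In the last bullet of protocol Section 7.4, ask for *vital status and any hospital readmission, invasive mechanical ventilation or ECMO through Day 28*, within the limits of the participant's consent. Record the source and date in the eCRF.
2. In Section 9.4.1, state that outcomes recovered this way are used in the primary analysis, and that failure is imputed only when status remains unknown.
3. Put the same rule in the SAP for Tables 18 and 19, and in the Phase 3 SAP. Without this, discontinuation before Day 25 remains an event in the Cohort 1/2 tables whatever the physician reports.
4. Reconcile the new request with the Section 7.4 bullet that treats an unreachable participant as withdrawn.

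The cost is a few sentences across the protocol and SAP and a short eCRF entry. No visit or procedure is added, because the physician contact is already asked for. The downside is that some outcomes will rest on a physician's report that may miss an admission elsewhere, so the recorded source should allow these to be identified.

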## 8. STUDY ASSESSMENTS AND PROCEDURES

Planned time points for all study assessments and procedures are provided in the Schedule of Assessments (see [Table 1](#)). Adherence to the study design requirements, including those specified in the Schedule of Assessments, is essential and required for study conduct. Protocol waivers or exemptions are not allowed.

Repeat or unscheduled samples may be taken for safety reasons or for technical issues with sample quality. Record results of any unscheduled assessments or visits related to study participation in the eCRF.

### 8.1. Screening

All screening evaluations must be completed and reviewed to confirm that potential participants meet all eligibility criteria.

Procedures conducted as part of the participant's routine clinical management (e.g., SARS-CoV-2, blood counts) and obtained before signing of the ICF may be utilized for screening or baseline purposes, provided the procedures meet protocol-specified criteria and were performed within the time frame defined in the Schedule of Assessments. Applicable results must be entered into the participant's eCRF.

The following examinations and procedures will be conducted as part of the screening process:

- Informed consent. Documentation of completion of the informed consent process with the potential participant (and/or legally authorized representative as applicable) (see [Section 11.1.3](#)).
- Demographics, medical history (including family medical history), medication history, physical examination, vital signs, height, and weight.
- Cardiac health: ECG (see [Section 8.3.3](#)), congestive heart failure history, clinical signs of pericarditis, and Tisdale risk score (see [Appendix 5](#)) (or plan for serial ECGs or continuous telemetry).
- Laboratory: Clinical chemistry, hematology, and coagulation (fibrinogen, D-dimer, aPTT, PT/INR) tests (see [Section 8.3.4](#)).
- Review of all eligibility criteria to determine if participant qualifies for randomization. This includes review of results of all screening assessments and a final review for any changes in medical history or concomitant medications.

### 8.2. Efficacy Assessments

The activity of dociparstat will be assessed by clinical evaluations and routine laboratory tests.

#### 8.2.1. Clinical Evaluations

The efficacy endpoints primarily rely on the participant's clinical status with respect to death, hospitalization, mechanical ventilation, and supplemental oxygen. The primary efficacy endpoint is the proportion of participants who are alive and free of invasive mechanical ventilation through Day 28 and the key secondary endpoint is all-cause mortality at Day 28.

Two of the secondary endpoints, clinical status and time to clinical improvement, are based on the 8-point NIAID ordinal scale (see [Appendix 4](#)). In addition to death, hospitalization, mechanical ventilation, and supplemental oxygen, components of the ordinal scale also include ongoing medical care and limitations on activities. It is important for changes in each of these components to be documented with the date and time of change. Participants must be considered a 3 or 4 on the scale to be eligible for enrollment, and an improvement of  $\geq 2$  grades is considered a treatment success.

### **8.2.2. Laboratory Assessments**

Multiple laboratory assessments will contribute to the evaluation of efficacy. For simplicity, these laboratory assessments are included in the list of safety labs in Section [8.3.4](#).

Instructions for collection, handling, and shipment of samples is included in the laboratory manual.

## **8.3. Safety Assessments**

Planned time points for all safety assessments are provided in the Schedule of Assessments (see [Table 1](#)).

The investigator will discuss any immediate safety concerns with the sponsor (or designee) upon occurrence or awareness to determine if the participant should continue or discontinue receiving study intervention.

Safety data will be monitored by an independent DMC on a routine basis (see Section [9.6](#)).

### **8.3.1. Physical Examinations**

Measure height and weight at screening. Complete a physical examination at screening as part of the review for eligibility for the study. Investigators should pay special attention to clinical signs related to the respiratory system and any other previous or ongoing serious illnesses. Record any clinically-relevant findings in the eCRF as medical history.

After the first dose of study intervention, record any clinically-relevant change(s) in physical examination (obtained during routine standard of care) findings in the eCRF as an AE(s).

### **8.3.2. Vital Signs**

Assess all vital signs (temperature, pulse rate, respiratory rate, blood pressure, and oxygen saturation) at screening as part of the review for study eligibility.

Monitor temperature from baseline through hospital discharge. Record date and time of each measurement.

Record any clinically-relevant findings prior to the first dose of study intervention as medical history in the eCRF. During the treatment period of the study, record any clinically-relevant change(s) in vital sign measurements (obtained during routine standard of care) in the eCRF as an AE(s).

### 8.3.3. Electrocardiograms

ECGs will be obtained using an ECG machine that automatically calculates the heart rate and measures PR, QRS, QT, and QTc intervals.

As specified in the Schedule of Assessments, 12-lead ECGs will be obtained at the following time points:

- Screening
- Day 3 ( $\pm 1$  day), unless participant is being monitored by continuous telemetry
- Additional readings may be necessary to monitor AEs and/or changes in ECG measurements (e.g., as described in Section 7)

At screening, 3 individual ECG tracings should be obtained as closely as possible in succession, but no more than 2 minutes apart. The full set of triplicates should be completed in less than 4 minutes. At subsequent time points, a single ECG tracing will be obtained, with a repeat tracing to confirm QTc intervals  $>450$  msec.

Refer to Section 5.2 for QTc-related criteria for participant exclusion and Section 7 for QTc-related criteria for interruption and discontinuation of study intervention.

At screening, as part of the review for eligibility for the study, record any clinically-relevant ECG findings as medical history in the eCRF. During the treatment period of the study, record any clinically-relevant change(s) in ECGs (obtained at protocol-specified time points or during routine standard of care) in the eCRF as an AE(s).

It is recommended that QTc be calculated using Fridericia's formula (QTcF) for all participants. If a study center does not have access to an ECG machine capable of calculating QTcF, then correction using an alternate formula may be used. All recordings for a single participant must use the same correction formula; therefore, if one formula is used at screening to determine eligibility for enrollment, that same formula must also be used during treatment to determine if criteria have been met for discontinuation of study intervention.

### 8.3.4. Clinical Laboratory Assessments

All required laboratory assessments must be conducted in accordance with this protocol and the laboratory manual. The timing and frequency of laboratory assessments are specified in the Schedule of Assessments (Table 1).

- The laboratory tests (clinical chemistry, hematology, and coagulation) listed in Table 4 will be performed by the study centers' usual local laboratory, unless otherwise specified.
- All laboratory reports will be filed with the source documents.
- Site personnel must enter results into the eCRF for the specified laboratory parameters (with units and relevant reference ranges) at each specified time point.
- The investigator must document their review of each laboratory report. Clinically-relevant abnormal laboratory findings at screening and before the first dose of study intervention will be recorded as medical history.

- Clinically significant abnormal changes occurring within 28 days after first dose of study intervention will be recorded in the eCRF as an AE(s).
  - These laboratory tests will be repeated (and recorded in the eCRF) until the values return to normal or baseline or are no longer considered clinically significant by the investigator.
  - If such values do not return to normal/baseline within a period of time judged reasonable by the investigator, the etiology should be identified.
  - The investigator may consult with the medical monitor for any questions.

Laboratory tests may be performed at additional times during the study as part of standard care, as determined necessary by the investigator, or as required by local regulations. Any laboratory test(s) performed in response to an AE must be recorded in the participants' eCRF (as an unscheduled visit if not at a protocol-specified time point).

Refer to Section 5.2 for laboratory-related participant exclusion criteria and Section 7 for laboratory-related criteria for interruption and discontinuation of study intervention.

Study center staff must enter results of all local/institutional laboratory results into the eCRF. Instructions for collection, handling, and shipment of samples for central analysis is included in the laboratory manual.

**Table 4: Laboratory Assessments**

Laboratory Assessments	Parameters for Routine Monitoring	Additional Parameters
Hematology (local)	
 
• Platelet Count
 
• Hemoglobin
 
• Absolute neutrophil count
 
• White blood cell count with differential
 
	Screening only: Hematocrit, red blood cell count
Clinical Chemistry (local)	
 
• Alanine aminotransferase
 
• Aspartate aminotransferase
 
• Total and direct bilirubin
 
• Alkaline phosphatase
 
• Blood urea nitrogen
 
• Creatinine (with calculated creatinine clearance or estimated glomerular filtration rate)
 
• Lactate dehydrogenase
 
• Calcium
 
• Magnesium
 
• Potassium
 
• Sodium
 
• C-reactive protein
 
• Ferritin
 
	Screening only: Chloride, phosphate, albumin, total protein, glucose, uric acid, gamma-glutamyl transferase
Coagulation (local)	
 
• Activated partial thromboplastin time
 
• Prothrombin time and international normalized ratio
 
• D-dimer
 
• Fibrinogen
 
• Anti-Xa (to monitor enoxaparin)
 
	
Other (plasma will be stored for analysis by central lab)	
 
• HMGB1
 
• IL-6
 
• TNF<math>\alpha</math>
 
• Serum amyloid A (SAA)
 
• Other biomarkers of inflammation
 
	
HIT Evaluation a (local)		Only when indicated: 
 
• Anti-PF4/heparin antibody (ELISA)
 
• Serotonin release assay (SRA)
 

a Refer to HIT evaluation algorithm and guidelines in [Appendix 6](#).

## **8.4. Adverse Events and Serious Adverse Events**

AEs will be reported by the participant (or, when appropriate, by a caregiver, surrogate, or the participant's legally authorized representative).

The investigator and any qualified designees are responsible for detecting, documenting, and recording events that meet the definition of an AE or SAE and remain responsible for follow-up.

AEs will be categorized by system organ class and preferred term using the Medical Dictionary for Regulatory Activities dictionary and AE severity will be graded according to the National Cancer Institute-Common Terminology Criteria for Adverse Events (NCI-CTCAE).

### **8.4.1. Time Period and Frequency for Collecting AE and SAE Information**

Any SAE that is considered related to study procedures will be collected from the time of consent until the first dose of study intervention. Any other medical occurrences that begin during this time period will be recorded on the medical history/current medical conditions section of the eCRF (not as an AE/SAE).

All AEs will be collected from the time of first dose (Day 1) through Day 28.

All SAEs will be recorded and reported to the sponsor or designee immediately and under no circumstance should this exceed 24 hours, as indicated in [Appendix 2](#). The investigator will submit any updated SAE data to the sponsor within 24 hours of the data being available.

Investigators are not obligated to actively seek new onset AEs or SAEs after the protocol-defined reporting period; however, if the investigator learns of any SAE and he/she considers the event to be reasonably related to the study intervention or study participation, the investigator must promptly notify the sponsor.

